## **5 STUDY PROCEDURES AND SCHEDULE OF EVENTS**

### **5.1 Enrollment**

Targeted enrollment is 150 subjects for this study. Study length is 2 years. Subjects will be assigned to 3T or 7T magnet to maintain a balance within the subgroups (primary with or without prior treatment and metastatic with or without prior treatment).

A subset of 25 of the 150 subjects will only undergo MRIs on the 7T magnet. We have recently performed upgrades to the magnet and need to test these new upgrades in order to get the best images to compare with the 3T magnet in the remaining subjects.

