### **6 IMAGING SCHEMA AND ACQUISITION**

#### **6.1 Schema**

##### **Day 1**

1. Standard precontrast anatomical MRI sequences at 3T and/or 7T: sagittal T1, coronal FLAIR, MPRAGE, axial T1, T2, T2\*, PD weighted images and DWI.
2. TOF angiography
3. Quantitative T1 images
4. DSC MRI (T2\* weighted) for perfusion with Gd bolus administration dose: 0.1mmol/kg)
5. Quantitative T1 images for permeability measurement will be performed 4 times
6. TOF angiography (postgadolinium)
7. Standard postgadolinium imaging at 3T and 7T: MPRAGE, axial T1, T2, T2\* weighted images.

A subset of 25 of the 150 subjects will only undergo MRIs on the 7T magnet.

[Section 6.1 and 6.2 numbers 4 and 5 will be assigned to either 3 or 7 Tesla. 1, 2, 3, 6 and 7 will be performed on both magnet fields, the order of the scanners will be balanced, see Study Procedures section 5.2.3.] In subjects who cannot tolerate long MRI study either 3T or 7T (MRI with no dynamic imaging) pre-contrast sequences 1, 2 and 3 maybe acquired on Day 2 (dash line in the figure below).

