### **9.2 Baseline Summaries**

Descriptive statistics will be provided for all baseline characteristics including demographic variables (age, gender, race), disease characteristics (prior treatment, baseline KPS and steroid use), tumor characteristics (size and permeability) and pre-imaging variables. For continuous data, mean and standard deviation and minimum, median and maximum will be estimated. For categorical variables, the number and percent for each category will be estimated.

Data from those subjects already enrolled will be summarized both separately from the rest of the subjects and combined with the other subjects. These first eleven subjects will be considered as feasibility subjects. Summaries of imaging measures will include data on relative normalized signal intensity changes (CNR) for dynamic MRI data sets, cerebral blood volume and relative mean transit time for the perfusion data and  $K^{trans}$  for vascular permeability.

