### **9.3 Descriptive Statistical Analyses**

All analyses described are viewed as descriptive in nature to better understand the variation in these parameters and not to provide definitive results as would be expected in a Phase III trial. The statistical analyses provide appropriate frameworks for assessing the relative magnitudes of effects while potentially controlling for other parameters of interest. Results will be used to plan for future definitive studies of the parameters that have appropriate power calculations and sample sizes. These analyses will be performed when target sample sizes are achieved and not on as interim analyses.

For Primary Aim 1, the primary descriptive comparisons are paired sample t-tests comparing the normalized signal intensity changes (CNR) for T1-weighted MRI signal at 3T and at 7T. Secondary analyses will use a repeated measures analysis of variance (ANOVA) model to compare 3T and 7T while adjusting for other factors including tumor type, prior therapy, and, potentially, important baseline factors that differ between the subjects assigned to the two field strengths. These tests are descriptive in nature and are not powered to provide a complete answer. Subjects who are scheduled to be imaged by a magnet of one field strength but are “crossed-over” to the other magnet or who otherwise fail to complete the scheduled imaging will not be included in these analyses. For the baseline characteristics, if two-sample tests of hypotheses indicate a significant difference ( $p<0.10$ ) between 3T and 7T signal intensity changes for a particular variable, that variable will be included in the ANOVA model as a covariate. Normality will be assessed graphically and, if needed, a transformation (e.g. the logarithmic transform) will be applied. These analyses will be performed for Gd T1-weighted MRI data only

For Primary Aim 2, the analyses will be similar to those for Aim 1 above using normalized (CNR) signal intensity decreases in the DSC data sets. . The same factors and analyses will be used. This objective assesses only Ferumoxytol.

For the first Secondary Aim, mixed model repeated measures ANOVA's will be fit. The outcomes will be relevant dynamic MRI (DCE and DSC) signal intensity changes for permeability and for perfusion. Factors will include imaging agent (Gd or ferumoxytol)

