and field strength (3T and 7T). Each subject will contribute one measure for each combination of imaging agent and field strength (4 measures total). This will not be a definitive analysis as the power cannot be determined *a priori*. The mixed model allows for estimation of the means and confidence intervals for imaging agent and field strength (57). These data will be used to plan future comparative studies. For the second Secondary Aim, blood volumes will be compared using repeated measures ANOVA to compare the imaging agents. For the third Secondary Aim, analyses will add covariates of prior therapy to the analyses listed above. For the comparisons between treated and untreated subjects, means and confidence intervals will be estimated for each group for the perfusion and permeability measures and for the baseline characteristics listed above. Since prior treatment is likely confounded with other variables (e.g. disease severity), these comparisons will also be descriptive in nature and mainly be used to plan future studies.

For Secondary Aim five, the pathology will be analyzed qualitatively for the presence of iron staining. The amount and localization of the staining will be assessed, with attention paid to whether the tumor cells themselves or reactive cells in and around the tumor demonstrate iron uptake.

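### Section 9.3 assumes dynamic data at both field strengths in each subject, but the schedule gives one, and Section 9 does not place the 25 7T-only subjects

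*Combined protocol and SAP*

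**What the plan says.** **Analysis (Section 9.3).** Aim 1 (gadolinium, T1-weighted CNR) is compared between 3T and 7T by paired t-tests, with a repeated measures ANOVA as secondary analysis. For Aim 2 (ferumoxytol DSC) the text says: "The same factors and analyses will be used". For the first secondary aim a mixed model is fitted: "The outcomes will be relevant dynamic MRI (DCE and DSC) signal intensity changes for permeability and for perfusion". Of the data for that model it says: "Each subject will contribute one measure for each combination of imaging agent and field strength (4 measures total". The one exclusion, given under Aim 1, is that crossed-over subjects and those "who otherwise fail to complete the scheduled imaging will not be included in these analyses".

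**Imaging schedule.** Section 6.1 says of the dynamic series that "numbers 4 and 5 will be assigned to either 3 or 7 Tesla"; the remaining items (1, 2, 3, 6 and 7) are done on both magnets. Sections 5.3.3 and 9.5 likewise place dynamic imaging at 3T or 7T according to the assigned group. Section 5.3.4 puts the Day 2 dynamic imaging on the scanner used on Day 1.

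**The 7T-only subset.** Section 5.1 says: "A subset of 25 of the 150 subjects will only undergo MRIs on the 7T magnet". The reason given is that the investigators "need to test these new upgrades in order to get the best images to compare with the 3T magnet in the remaining subjects". Sections 5.3.3, 5.3.4, 5.3.5 and 6.1 repeat the subset; Section 9 does not mention it. Section 9.2 does deal with another set-up group: "These first eleven subjects will be considered as feasibility subjects", and their data are summarised both apart from and together with the rest.

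**The concern.** The analysis text and the schedule describe different designs. A paired test, or a model expecting all four agent-by-field cells from each subject, treats field strength as varying within the subject. The schedule makes it vary between subjects for dynamic outcomes. For Aim 2 the named primary comparison cannot be run on the data of a single visit. An analyst would have to choose a replacement after the data are in, and Section 9.3 gives no guide to that choice.

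The choice also decides what happens to the 25 upgrade-testing subjects. Once the field contrast is made between subjects, nothing in Section 9 keeps their scans out of the 7T group. Section 9.3 says that the results will be used to plan definitive studies, so both the 7T mean and the type of variance carried forward matter.

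**Working it through.** **Inputs.** 150 subjects and 25 scanned only at 7T (Section 5.1); two agents; one magnet for items 4 and 5 (Section 6.1); the same scanner for dynamic imaging on Days 1 and 2 (Section 5.3.4). The split of the other subjects between magnets is not given. I assume 1:1 and show a range from 60% to 40% assigned to 7T.

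**1. Measures per subject.**
- Plan's figure: 2 agents x 2 field strengths = 4 per subject, or 150 x 4 = 600 per outcome.
- Schedule: 2 agents x 1 field strength = 2 per subject per visit, or at most 150 x 2 = 300 per outcome for one visit each.
- One-day crossing (Section 5.6): gadolinium at one field and ferumoxytol at the other, still 2, and no agent is seen at both fields.
- Repeat visits: Section 5.3.1 allows them, but no section plans a change of magnet between visits.

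The plan's 4 cannot be reproduced for dynamic outcomes.

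**2. Pairs for the paired t-test.**
- Aim 2: the ferumoxytol DSC series (Day 2, item 4) is on one magnet, so there are no within-visit 3T/7T pairs for anyone.
- Aim 1: if CNR comes from the quantitative T1 series (item 5), again no pairs. If it comes from the standard post-gadolinium T1-weighted images (item 7), pairs exist in up to 150 - 25 = 125 subjects. Section 9.3 does not say which images are used.

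Other parts of the plan read as between-subject: Section 9.3 adjusts for baseline differences between those assigned to each field strength and screens covariates with two-sample tests, and Section 9.5 speaks of 3T and 7T groups.

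**3. Where the 25 go.** A 7T-only subject who completes the planned scans has neither crossed over nor missed scheduled imaging, so the exclusion rule does not remove that subject.
- Paired test: dropped, because there is no 3T value.
- Mixed model for the first secondary aim: included, at 7T only.
- A between-subject analysis for Aim 2: included, at 7T only.

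**4. Their share of the 7T group, and the cost of leaving them out.** With n7 and n3 the numbers of the other 125 at each field:
- Share = 25/(n7 + 25).
- Ratio of confidence interval widths, excluded to included, assuming equal SD and no crossover = sqrt[(1/n7 + 1/n3) / (1/(n7 + 25) + 1/n3)].

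| Other 125 at 7T (assumed) | n7, n3 | Share of 7T group | Width ratio |
|---|---|---|---|
| 60% | 75, 50 | 25/100 = 25% | 1.054 |
| 50% | 62.5, 62.5 | 25/87.5 = 29% | 1.080 |
| 40% | 50, 75 | 25/75 = 33% | 1.118 |

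If mean CNR in the 25 differs by d from that of the other 7T subjects, including them moves the 7T mean by share x d, that is 0.25d to 0.33d. The documents give no value or sign for d.

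**The case against.** Five points deserve an answer.

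- **The paired test already drops the 25.** This stands. A reader might infer that Section 9.3, followed to the letter, puts them into the Aim 2 primary comparison. It does not: as written that comparison is paired, and they have no pair. They enter through the mixed model, or through the between-subject analysis that must replace the Aim 2 test.
- **A mixed model does not need four cells.** Also true. With a subject random effect and one field per subject, field strength is estimated from between-subject information. The documents do not show that the model's estimates or variances would be wrong; they show that its data are misdescribed.
- **Section 5.1 already settles who is compared.** Its most natural reading confines the 3T comparison to the other 125, but it could also mean comparing 7T images with 3T images from those subjects. Even on the first reading, it explains a purpose and does not define an analysis set.
- **Some T1 data exist at both fields.** Section 7.3 uses quantitative T1 at 24±6 hours, and Day 3 imaging is on both magnets. Ferumoxytol therefore has some permeability-related data at both fields. This does not restore four dynamic measures, and it gives the 25 no 3T data.
- **The study is descriptive.** It is, and that limits the weight of the point. It does not make a paired test possible where there are no pairs.

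**Conclusion.** The point holds. For dynamic outcomes each subject gives 2 measures per visit, not 4, and the field-strength contrast is between subjects. The paired test carried over to Aim 2 has no within-visit pairs. For Aim 1 it is usable only if CNR comes from images taken on both magnets. These conclusions follow from the schedule and need no assumption beyond the absence of any planned magnet switch at repeat visits.

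The omission of the 25 is a real gap of smaller weight. They would form about 29% of the 7T group in the mixed model or in a between-subject Aim 2 analysis (25% to 33% over the assumed splits). It would be tempting to say that the 7T result is therefore biased. The documents do not support that, because they do not say whether upgrade-testing scans have higher or lower CNR than later ones. The exclusion of crossed-over subjects is pre-specified, agrees with Section 5.6, and is not in dispute.

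**What to change.** Amend Section 9.3 in three places.

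1. Correct the sentence on four measures: for dynamic outcomes, one measure per agent per visit at a single field strength, with agent as a within-subject factor, field strength as a between-subject factor, and a subject random effect that also covers repeat visits.
2. For Aim 2, replace the paired t-test with a two-sample comparison adjusted for tumor type and prior therapy. For Aim 1, keep the paired test only if CNR is taken from the post-gadolinium T1-weighted images acquired on both magnets (Section 6.1, item 7), and say so; otherwise use the same between-subject comparison.
3. State that the 25 7T-only subjects are summarised separately and left out of the main 3T/7T comparisons, with a combined analysis as a sensitivity analysis, in line with the two-way reporting in Section 9.2 for the feasibility subjects. State that at most 125 subjects inform the main comparisons.

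The change is to text only; scanning, enrolment and the crossover rule stay as they are. The cost is a confidence interval for the dynamic field contrast about 8% wider at 1:1 (5% to 12% over the assumed splits). Replacing the Aim 2 paired test gives up no within-visit pairing, because none exists.

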1.2.4 To describe the microscopic distribution of ferumoxytol particles in tissue

## 2 BACKGROUND

### 2.1 The blood-brain barrier in CNS tumors

The BBB is an anatomical feature of CNS capillaries that consists of a continuous layer of endothelial cells bound together with tight junctions that allow very little transcellular or pericellular leakage of blood-borne molecules (5, 36). In normal brain, the BBB limits permeability based on electric charge and lipid solubility, and normally excludes molecules of greater than  $M_r$  180. The neurovascular unit is a new, integrated approach

to thinking about and working with the BBB. It is comprised not only the BBB endothelial cells but also the basement membrane, pericytes, microglia and astrocytic foot processes in the capillary microenvironment. Local environmental and cellular factors and the varying integrity of the neurovascular unit impact barrier permeability in tumors of the CNS, both before and after treatment. Brain tumors often have a leaky blood-tumor barrier (BTB) because the neovasculature in the tumor lacks some BBB characteristics (5). The barrier in the brain around malignant tumors can have variable permeability due to neovascularization, inflammation, and gliosis. The well-vascularized, actively proliferating edge of the tumor is particularly variable and complex in terms of barrier integrity (18, 29, 36).

Cancer treatments such as steroids, chemotherapy, radiotherapy, or anti-angiogenesis therapy induce changes in tumor vasculature, tumor permeability, and tumor cell viability. Many of these effects will occur hours to days after treatment, but changes in gross tumor volume can only be measured at later times (several days to weeks). Methods to measure early anti-tumor effects would be useful in predicting outcomes and modifying therapies to maximize response.

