**5.3.4 Day 2**

Imaging

- Anatomical imaging on 3T & 7T and dynamic MRI (with ferumoxytol, see section 4.2). A subset of 25 of the 150 subjects will only undergo MRIs on the 7T magnet.
- Dynamic imaging will be performed on the same scanner as on which the dynamic the dynamic imaging was acquired on Day 1(as described below on Section: 6.0). Ferumoxytol Administration:
  - The ferumoxytol will be diluted 1:2 to make a 10mg/ml solution. The dose of ferumoxytol will be 4 mg/kg (to a maximum of 510 mg), and will be administered intravenously on day 2.
  - Dose 1: Give 1/4th of the total dose (1mg/kg); inject at up to 3 ml/sec followed by a saline flush. This rate is required for adequate signal change during the dynamic imaging.
  - Dose 2: Give 3/4th of the total dose (3mg/kg); inject no faster than 1 ml/sec and followed by a saline flush
  - 
  - The dilution and injection parameters of the ferumoxytol may be adjusted to obtain optimal signal changes on MRI/MRA and to decrease the possibility of an allergic reaction. Injection rate can be varied based on the participant's IV site, but the total dose will never exceed 510mg.

Monitoring

- A clinical examination will be performed before and after the MRI session on Day 2.. Blood pressure and pulse will be monitored before the first dose of ferumoxytol and after each dose of ferumoxytol, and at 30 minutes after the initial dose of ferumoxytol.

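### The secondary 3T-versus-7T models choose extra covariates by an unclear p<0.10 screen; a short fixed list would do better where each subject is imaged at one field strength, mainly Aim 2

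*Combined protocol and SAP*

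**What the plan says.** Section 9.3 plans paired t-tests as the primary comparison for Aim 1 and a repeated-measures ANOVA as the secondary one. The ANOVA adjusts for tumor type and prior therapy and, potentially, for important "baseline factors that differ between the subjects assigned to the two field strengths". The only operating rule for those extra factors is that, if two-sample tests differ at p<0.10 "between 3T and 7T signal intensity changes for a particular variable, that variable will be included in the ANOVA model as a covariate". For Aim 2 the plan says: "The same factors and analyses will be used".

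The candidates come from Section 9.2: age, gender, race, baseline KPS and steroid use, then "tumor characteristics (size and permeability) and pre-imaging variables". Prior treatment is also listed there but is already in the model.

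Section 6.1 (Day 1) says that imaging items "numbers 4 and 5 will be assigned to either 3 or 7 Tesla", whereas "1, 2, 3, 6 and 7 will be performed on both magnet fields". Item 4 is the DSC series and item 5 the repeated quantitative T1 series. For Day 2, when ferumoxytol is given, Section 5.3.4 adds: "Dynamic imaging will be performed on the same scanner". Under Sections 5.2.3 and 9.5 the magnet is not randomised, and it may depend on which scanner is available.

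**The concern.** The sentence cannot be carried out as written. It begins with baseline characteristics but puts the test on the signal intensity change, which is the outcome. The earlier clause in the same paragraph suggests that a test of baseline imbalance was meant. Such a test says nothing about whether a variable predicts CNR. At this sample size it also misses moderate imbalances more often than it finds them.

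The protocol itself points to likely predictors. Section 2.1 says: "Cancer treatments such as steroids, chemotherapy, radiotherapy, or anti-angiogenesis therapy induce changes in tumor vasculature, tumor permeability, and tumor cell viability". Section 1.1 names tumor size among the factors whose impact is to be studied. Yet steroid use and size are adjusted for only if the test flags them.

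The same rule can let in permeability. Section 9.2 does not say how baseline permeability is measured, and the only Day 1 permeability series described is post-contrast on the assigned magnet. The 24-hour quantitative T1 scan is done on both magnets but is also post-contrast. A covariate measured on the assigned scanner could absorb part of the field-strength effect being estimated.

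At stake are the width and bias of the adjusted 3T-versus-7T estimates, which Section 9.3 intends for planning later definitive studies.

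**Working it through.** The plan has no figure to reproduce: Section 9.4 states that the sample size has no statistical basis, and no SD, effect size or correlation is given. The effect, correlations and imbalances below are therefore assumptions.

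**Inputs.** 150 subjects (Section 9.4), less 25 imaged on 7T only (Section 5.1), less up to 20% lost to crossover or non-completion (Sections 5.2.3, 5.6): (150 − 25) × 0.8 = 100, or 50 per magnet; 40 and 60 were also tried. The model is a two-group linear model with one observation per subject, and tumor type and prior therapy are always included. The true field effect is 0.50 SD. A covariate enters if its two-sided t-test gives p<0.10 (the plan does not state sidedness).

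**1. How often the screen fires.** For a true imbalance of d SD the test is noncentral t with noncentrality d√(n/2). For d = 0.2 and n = 50 this is 0.2 × 5 = 1.0, and the flag probability is 26% (23% at n = 40, 29% at n = 60). At n = 50 it is 44%, 64% and 80% for d = 0.3, 0.4 and 0.5. With no real imbalance, seven candidates (age, gender, race, KPS, steroid use, size, permeability) and independent tests, at least one enters with probability 1 − 0.9⁷ = 52%.

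**2. Expected values.** The 95% interval width is about 2t√(2/n)√(1 − R²). Unadjusted at n = 50: 2 × 1.985 × 0.2 = 0.794 SD. With one covariate at r = 0.5: 0.794 × √0.75 = 0.688. Bias with no adjustment is r × d per covariate: 0.3 × 0.2 = 0.06 and 0.5 × 0.2 = 0.10. For four covariates at r = 0.3 it is 4 × 0.06 = 0.24.

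**3. Simulation, 50 per magnet** (6,000 runs per cell with one covariate, 4,000 with four):

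| Setting | Unadjusted | Rule | Always adjusted |
|---|---|---|---|
| Width, one balanced covariate, r = 0.3 | 0.793 | 0.791 | 0.760 |
| Width, one balanced covariate, r = 0.5 | 0.791 | 0.781 | 0.689 |
| Width, four balanced, each r = 0 | – | 0.797 | 0.807 |
| Width, four balanced, each r = 0.2 | – | 0.795 | 0.744 |
| Width, four balanced, each r = 0.3 | – | 0.785 | 0.648 |
| Estimate, one imbalanced 0.2 SD, r = 0.3 | 0.557 | 0.522 | 0.497 |
| Estimate, one imbalanced 0.2 SD, r = 0.5 | 0.602 | 0.545 | 0.501 |
| Estimate, four imbalanced 0.2 SD same way, r = 0.2 | 0.655 | 0.565 | 0.496 |
| Estimate, four imbalanced 0.2 SD same way, r = 0.3 | 0.739 | 0.603 | 0.499 |

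With one covariate the rule removes 55–61% of the bias across n = 40 to 60, and its intervals still cover 95.5–95.6% at n = 50. With four imbalanced covariates coverage is 94.2% (r = 0.2) and 93.4% (r = 0.3).

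**4. Permeability** (n = 50; r = 0.3 / 0.5). If the scanner alone shifts measured permeability by 0.2 SD, the estimate is 0.50 / 0.50 with permeability left out, 0.46 / 0.44 under the rule and 0.44 / 0.40 if always adjusted. If the 0.2 SD difference is real, these become 0.56 / 0.60, 0.53 / 0.54 and 0.50 / 0.50. With neither, the choice makes no difference to the estimate.

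**5. Within-subject contrast.** In 60 simulated data sets of 50 subjects measured at both strengths, adding a subject-level covariate to the mixed model changed the field estimate by at most 2 × 10⁻¹⁵ and its standard error by at most 2 × 10⁻⁶.

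**6. Literal reading.** If the test is on the outcome, one test governs every variable, so all enter or none do. At 50 per magnet they enter with probability 10%, 44% and 80% for a true field difference of 0, 0.3 and 0.5 SD.

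**7. Separate check with other inputs.** This used three prognostic and four irrelevant covariates at 50 per magnet, with a fixed list of the three prognostic ones. Power for a 0.5 SD effect, rule versus fixed list, was 68.6% v 68.2% at R² = 0, 69.4% v 72.9% at 0.1 and 71.1% v 83.0% at 0.3. With a 0.3 SD imbalance in each prognostic covariate, R² = 0.3 and no true effect, bias was +0.083 v −0.002 SD and type I error 6.4% v 5.0%. Unadjusted, they were +0.284 SD and 28.8%.

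**The case against.** The strongest reply is that the harm arises in a model the plan does not state. Section 9.3 specifies paired and repeated-measures analyses, and in a within-subject contrast the covariates cancel (step 5). That holds for the primary t-test and for any Aim 1 contrast built on the static sequences run on both magnets. It does not hold for Aim 2: the DSC series exists at one strength per subject, so the comparison is between subjects whatever the model is called. Aim 1 may be touched too, if it uses the repeated quantitative T1 series (item 5), which is also on one magnet. The conflict between paired analysis and single-magnet acquisition is a separate matter; settling it would not make the screen a good rule.

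The remaining points largely stand as limits. The correlations and imbalances are assumed. At r = 0.3 with one covariate the loss is about 4% in width or 0.02 SD of bias, and the larger figures need stronger or several predictors. Section 2.1 links steroids to vasculature and permeability, not directly to DSC CNR, and nothing in the documents links age or KPS to CNR; their inclusion is conventional and cheap. The 52% chance-entry figure shows that the model is unpredictable, not biased. Equal groups of 50 are a simplification, because Sections 5.2.3 and 9.5 expect more loss at 7T, Section 5.6 keeps a subject crossed over on one day for the other aim, and visits may repeat.

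**Conclusion.** The concern holds. The rule needs rewriting on any reading. Under the sensible one, for a comparison with one field strength per subject, it gives up most of the precision available from a prognostic covariate and leaves roughly 40–45% of the bias from a real imbalance. It is not useless: coverage stays near 95% with one confounder. With four covariates at an assumed r = 0.3, a fixed list gives intervals about 17% narrower (0.648 against 0.785 SD) and removes a 0.10 SD bias under same-direction imbalances of 0.2 SD. The gain vanishes if the covariates do not predict CNR.

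The permeability problem is probably minor for Aim 2: Section 1.1 predicts better precision at 7T rather than a shift in the measured value, and Section 2.3 expects little first-pass leakage of the iron agent. Neither approach deals with unmeasured differences from availability-based assignment or from dropping crossed-over subjects. This is a worthwhile improvement to a secondary, descriptive analysis and does not threaten the primary comparison.

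**What to change.** Delete the p<0.10 sentence in Section 9.3 and state instead:

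- The secondary 3T-versus-7T models for Aims 1 and 2 always include tumor type, prior therapy, steroid use, tumor size, age and KPS.
- Tumor size has one source and one method for every subject, for example two dimensions on the standard MRI used for eligibility, because Section 7.1 lets the measuring sequence vary by lesion. Add a rule for lesions that are evaluable but not measurable, which Section 3.1 admits.
- Gender, race and any pre-imaging variable named in advance are described by field-strength group and added together in one sensitivity model.
- Permeability measured on the assigned scanner is left out of the model that estimates the field effect. Its relation to CNR, a goal in Section 1.1, is reported separately. A permeability-adjusted model is given as a sensitivity analysis, since a real imbalance would otherwise go unadjusted.

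The cost is a change of wording and about four degrees of freedom out of roughly 100. If none of the four covariates relates to CNR, the interval widens by about 1% (0.807 against 0.797 SD), assuming complete covariate data. Age, KPS and steroid use are already listed in Section 9.2; size may have to be re-measured on existing scans. No visit, procedure or sample size changes.

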#### **5.3.3 Day 1**

##### **Laboratory testing:**

- creatinine to calculate GFR prior to gadolinium administration (may be done up to 3 weeks prior)

- Urine pregnancy test in women of child bearing potential.

Imaging:

- Anatomical imaging on 3T & 7T and dynamic MRI (with gadolinium, see section 4.1) on either 3T or 7T (dependent on which group subject is assigned and as described in section 5.1.3)
- Day 1 and Day 2 imaging sessions may be separated by up to 7 days.
- A subset of 25 of the 150 subjects will only undergo MRIs on the 7T magnet.

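### Section 9.3 carries a paired 3T/7T t-test over to Primary Aim 2, where the schema plans no pairs; the four-measure count for the first Secondary Aim is wrong for its dynamic outcomes for the same reason

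*Combined protocol and SAP*

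**What the plan says.** **Analysis text (Section 9.3).** For Primary Aim 1, "the primary descriptive comparisons are paired sample t-tests comparing the normalized signal intensity changes (CNR") at 3T and at 7T. The second primary aim is then covered by reference back: "the analyses will be similar to those for Aim 1 above using normalized (CNR) signal intensity decreases in the DSC data sets", followed by "The same factors and analyses will be used. This objective assesses only Ferumoxytol". The exclusion rule begins "Subjects who are scheduled to be imaged by a magnet of one field strength": those moved to the other magnet, or who do not complete their scheduled imaging, are left out. For the first Secondary Aim the outcomes are dynamic DCE and DSC signal changes, and "Each subject will contribute one measure for each combination of imaging agent and field strength (4 measures total").

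**Imaging text.** Section 5.3.3 plans "dynamic MRI (with gadolinium, see section 4.1) on either 3T or 7T" on Day 1, according to the subject's group. For Day 2, Section 5.3.4 says "Dynamic imaging will be performed on the same scanner as on which the dynamic" imaging of Day 1 was done. In Section 6.1, item 4 is the DSC series and item 5 the serial quantitative T1 series, and "Section 6.1 and 6.2 numbers 4 and 5 will be assigned to either 3 or 7 Tesla"; the other items are done on both magnets. Section 9.5 likewise assigns dynamic imaging to one field per subject.

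**The concern.** A paired t-test needs both members of the pair in the same subject. For Primary Aim 2 that means ferumoxytol DSC at 3T and at 7T in one person. If the schema collects it at only one field, the analysis named for one of the two primary aims has no data to run on. Someone would then have to choose a replacement after the data are in.

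The Secondary Aim sentence presents field strength as a within-subject factor for the same kind of data. Section 9.3 says the results will be used to plan later studies. A between-subject variance and a paired-difference variance are different quantities, so the plan should say which one the trial estimates.

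**Working it through.** **1. Ferumoxytol DSC pairs.** Each route by which a subject could have ferumoxytol DSC at both fields:

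| Possible route | What the protocol plans | Pairs |
|---|---|---|
| Both magnets within Day 2 | One ferumoxytol DSC series, on the Day 1 dynamic scanner, with the remaining dose given after it (5.3.4, 6.1) | 0 |
| Option A (6.2.1) | One magnet on Day 2 | 0 |
| Option B (6.2.2) | Two magnets on Day 2, but Section 6.1 applies the one-field rule to 6.2 as well and lets only pre-contrast items 1 to 3 move to Day 2 | 0 |
| Day 3 | No contrast given (5.3.5) and no DSC listed (6.1) | 0 |
| Repeat visits (5.3.1) | Visits may be repeated, with no planned change of field | 0 |
| Crossover (5.6) | Unplanned, and excluded by 9.3 | 0 |
| 7T-only subset of 25 (5.1) | No 3T scan at all | 0 |

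Planned pairs: 0 of 150.

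**2. Measures per subject, first Secondary Aim.** The plan's figure is a full crossing: 2 agents × 2 fields = 4. The schema gives 2 agents × 1 assigned field = 2 per visit, for DSC (item 4) and again for the serial T1 series (item 5). For one visit and one such outcome:

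- 150 − 25 = 125 subjects assigned to 3T or 7T: 125 × 2 = 250 observations, against 125 × 4 = 500 as written.
- All 150 subjects: 150 × 2 = 300, against 150 × 4 = 600.

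**3. What can be estimated.** Take the 125 assigned subjects with two measures each.

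- With a separate effect for every subject, the design matrix has 125 + 1 (agent) + 1 (field) = 127 columns and rank 126. The field column is the sum of the indicators of the 7T subjects, so no within-subject field effect can be estimated.
- Without subject indicators, the columns are intercept, agent, field and their interaction: 4 columns, rank 4. All four cells are filled across subjects, so a mixed model can be fitted with field between subjects.

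**4. Illustration only.** The plan gives no SD or precision target. The half-width of a between-group 95% confidence interval, in SD units, is t(0.975, n₁+n₂−2) × √(1/n₁ + 1/n₂). Assuming an even split of the 125 (62 and 63), this is 0.35. If 20% are lost evenly (50 and 50), it is 0.40. Steps 1 to 3 do not depend on these figures.

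**The case against.** **The study is descriptive.** Section 9.3 says its tests are not powered to give a complete answer, Section 9.4 disclaims any basis for the sample size, and Section 9.5 says this is not a definitive trial. Section 9.3 also already uses between-subject language: two-sample tests, and baseline factors that differ between the groups assigned to each field. The slip would surface as soon as the data were handled. All of this limits the consequence, and it rules out reading the point as a failed power claim. It does not make the paired test computable, and the between-subject wording elsewhere shows that the paired test is the part that does not fit.

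**The Aim 2 analyses are only called similar.** The next sentence calls them the same, and no other test is named.

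**Permeability data do exist at both fields.** This stands in part. Section 7.3 counts the quantitative T1 at 24±6 hours as part of permeability evaluation, and Section 6.1 takes it on both magnets. A reader might infer that every permeability measure is limited to the assigned field. The documents do not support that. The correction from 4 to 2 covers DSC and the serial post-contrast T1 series. The 24-hour scan does not restore the count of 4 either: it is a single post-ferumoxytol time point, with no 24-hour gadolinium scan to match it.

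**Aim 1 uses the same test.** A reader might infer that its paired test fails too. Pre- and post-gadolinium T1-weighted images are planned on both magnets (Section 6.1, items 1 and 7), so a paired CNR is possible there outside the 7T-only subset. Section 9.3 does not name the sequence, and Sections 1.1.1 and 9.2 lean towards dynamic data. That is a question of clarity and not part of this error.

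**The Option B figure.** The Section 6.2 figure was not readable here, so what the second Day 2 magnet acquires rests on the wording of Section 6.1.

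**Conclusion.** The point holds for Primary Aim 2. The schema plans 0 within-subject 3T/7T pairs of ferumoxytol DSC data, under Option A or B, so the named primary analysis cannot be computed. This is a count from the protocol's own text. It assumes only that the one-field rule in Sections 5.3.4, 6.1 and 9.5 is followed and that repeat visits keep the assigned field, since no change is described.

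For the first Secondary Aim, the stated 4 measures is twice what the schema gives for the dynamic outcomes named there: 2 per visit for DSC and 2 per visit for the serial T1 series. This is the smaller correction. A reader might conclude that the mixed model is invalid, but it can be fitted once field strength is treated as a between-subject factor.

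**What to change.** Reword Section 9.3 in two places.

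1. **Primary Aim 2.** Replace the carried-over paired t-test with one named primary analysis: a linear model of ferumoxytol DSC CNR on field strength, adjusted for tumor type and prior treatment. Use one visit per subject, for example the first evaluable visit, because visits may be repeated. Base it on the subjects assigned to 3T or 7T. Summarise the 25 7T-only subjects, who are there to test the magnet upgrades, separately or in a sensitivity analysis.
2. **First Secondary Aim.** State 2 measures per visit for DSC and for the serial dynamic T1 series, one per agent, both at the assigned field. Fit the mixed model with agent within subject, field strength between subjects, a random subject effect, and a visit term if repeat visits are used. Keep the 24-hour ferumoxytol quantitative T1 as a separate within-subject comparison of 3T and 7T.

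The cost is a text amendment to Section 9.3. Imaging, enrolment and sample size are unchanged.
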